Given that the proposed study will exclude those taking **concomitant** medications with high risk of prolonging QT ([section 5.4.1](#)), we do not feel that electrocardiograms (EKGs) at study entry or during treatment are needed. **We believe that** exclusions on the basis of baseline QTc are unlikely to add significantly to **overall safety, above and beyond the planned exclusion** of participants with higher risk for drug-induced ventricular arrhythmias and cardiac events **based upon** relevant personal or family cardiac history, high risk clinical history including severe renal and liver disease, and those who are taking additional QTc prolonging agents. Further, in the midst of a global pandemic, the risk-benefit assessment must consider a wide range of participants, study staff and resource utilization-related issues. In this case, the condition of TdP is expected to be very rare and the performance of EKGs would require the use of personal protective equipment (PPE), for which supplies must be carefully preserved as the current pandemic escalates, and the risk of additional direct contact between staff and highly infectious study participants. As a result, we feel that the potential benefit of HCQ plus Azithro treatment for a disease with an overall case fatality rate of up to 3% (and based on preliminary estimates in the US, 3-11% among persons aged 65-84 years) outweighs the very small risk of a treatment-related cardiac AE, and therefore do not feel that EKGs at study screening or during treatment would be justified [50, 51].

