The combination of short-course chloroquine and Azithro has been observed to be well tolerated in malaria trials. In particular, Kimani et al studied malaria prevention during pregnancy where 1445 women received 3 days of chloroquine plus Azithro that was repeated at 4-8 week intervals during the second and third trimester of pregnancy. Although QT intervals were not assessed at baseline or throughout the study, there were no reported cardiac AEs [29], which would be the main danger signal for TdP in such a study. Further, Sagara et al. conducted two randomized, comparative, non-inferiority studies in Africa where patients with malaria received Azithro 1000 mg (n=227) or Azithro 500 mg (n=9) with chloroquine 600 mg base, all once daily for 3 days **and there were no treatment-related cardiac events** [49]. Given the extensive experience in malaria prophylaxis and treatment, it is clear that any QT prolongation by either drug is not likely to be clinically relevant. In fact, the WHO explicitly states “Despite hundreds of millions of doses administered in the treatment of malaria, there have been no reports of sudden unexplained death associated with quinine, chloroquine or amodiaquine, although each drug causes QT/QTc interval prolongation” [38].

Despite the low risk of clinically relevant QT prolongation, the proposed study design incorporates a number of measures to further reduce the risk. These include the exclusion of people who take other agents known to prolong QTc, have a personal or family history of Long QT syndrome, a history of ventricular arrhythmias, known structural or ischemic heart disease, or severe kidney or liver disease.

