The use of mobile devices that can perform ECG and measure vital signs has been discussed extensively by the study team and team leads have discussed the capabilities of select devices with their manufacturers or researchers who have used them. Based on these discussions, we have chosen to not include such monitoring for safety purposes for several reasons. Foremost, real-time monitoring for the large number of participants who will be enrolled at any one time will likely be unmanageable, and our older participants may have a harder time with such devices. Therefore, such monitoring is unlikely to lead to an immediate intervention. In addition, given the short duration of treatment and the long half-life of HCQ and Azithro, discontinuation of these drugs following detection of QTc prolongation, even if feasible, may have limited impact.

To help mitigate the risk of HCQ and Azithro causing TdP, we have followed the guidance from Simpson et al. [74b], which states, “minimizing exposure/contact: It may be reasonable to forego ECG screening to allow patients to remain in quarantine if no high-risk features exist (history of long QT syndrome, concomitant QT prolonging medications, structural or ischemic heart disease,

history of prolonged QTc on any ECG, history of abnormal renal function and/or electrolytes.” Therefore, we will exclude potential participants with underlying conditions associated with TdP, including: history of ventricular arrhythmia or on antiarrhythmics, personal or family history of long QT syndrome, history of hypomagnesemia or hypokalemia, history of structural or ischemic cardiac disease, use of antiepileptic or loop diuretic drugs, or use of drugs that can also prolong the QT interval. We will also have the close monitoring by the DSMB that can assist in quickly identifying safety issues with HCQ.

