4.2 Exclusion Criteria

(Medical history can be by self-report. Refer to the A5395 MOPS.)

- 4.2.1 Need for hospitalization or immediate medical attention in the clinical opinion of the study investigator.
- 4.2.2 History of or current hospitalization for COVID-19.

NOTE: Individuals hospitalized and then discharged, even if only hospitalized for 1 day, are excluded.

4.2.3 History of ventricular arrhythmia or **using antiarrhythmics within the past 30 days**.

4.2.4 Personal or family history of Long QT syndrome.

4.2.5 History of kidney disease.

NOTE A: If the individual responds “yes” but can provide a creatinine clearance (**CrCl**) value **of** ≥ 45 mL/min by Cockcroft-Gault equation **from** within 1 year **of** study entry, the individual may participate.

NOTE B: Please refer to the A5395 PSWP for the website link to the Cockcroft-Gault calculator.

4.2.6 History of ischemic or structural heart disease.

4.2.7 History of hypokalemia or hypomagnesemia or taking potassium supplementation or magnesium supplementation.

4.2.8 Personal medical history of porphyria, retinopathy, severe hepatic impairment, or G6PD deficiency.

4.2.9 Use of drugs with possible anti-SARS-CoV-2 activity within 30 days prior to study entry, e.g., remdesivir, lopinavir/ritonavir fixed dose combination, ribavirin, chloroquine, hydroxychloroquine, and azithromycin, or participation in a clinical trial involving any of these drugs whether for treatment or prophylaxis.

4.2.10 Requirement or expected requirement for a medication that significantly prolongs QT intervals or increases risk for QT prolongation (medications summarized in [section 5.4](#)), from 96 hours prior to study entry through 4 weeks after discontinuation of study treatment **except for escitalopram, citalopram, maprotiline, SC/IM risperidone, carbamazepine, ethosuximine, and zonisamide, which should not be used within 7 days prior to study entry.**

4.2.11 Loop diuretics are exceptions to exclusion criterion 4.2.10 but these cannot be used within 30 days prior to study entry.

4.2.12 Participating in a study where co-enrollment is not allowed.

4.2.13 Receipt of a SARS-CoV-2 vaccination prior to study entry.

4.2.14 Known allergy/sensitivity or any hypersensitivity to components of HCQ, azithromycin, or their formulation.

4.2.15 Active drug or alcohol use or dependence that, in the opinion of the site investigator, would interfere with adherence to study requirements

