6.3.4 Medical History

The medical history must include all signs and symptoms regardless of grade and all diagnoses identified by the ACTG criteria for clinical events and other diagnoses regardless of grade within the past 14 days. In addition, the following diagnoses should be recorded regardless of when the diagnosis was made (**verbal history is acceptable**):

- Hypertension
- Chronic obstructive pulmonary disease
- “Severe Obesity” (BMI > 40)
- Epilepsy requiring medications

- **Kidney disease**
- **Liver disease**
- Immunosuppressive conditions
- Reactive airway disease, Asthma
- Autoimmune disease
- Inflammatory bowel disease
- AIDS-defining conditions
- HIV infection
- Bone fractures (verbal history accepted)
- Coronary heart disease
- Heart failure
- Myocarditis
- Arrhythmias
- Valvular heart disease
- Stroke
- Cancer (exclusive of basal/squamous cell skin cancer)
- Diabetes
- Tuberculosis
- Chronic hepatitis C
- Chronic hepatitis B
- Pregnancy history
- If known by participant if they have been diagnosed with an acute viral respiratory infection (influenza, parainfluenza, respiratory syncytial virus, rhinovirus) within the previous 14 days.

A Smoking Status questionnaire will be completed at the **entry** visit as part of medical history and recorded on the eCRF. The questionnaire is posted on the DMC Portal in the Forms Management Utility.

Any allergies to any medications and their formulations must also be documented.

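### Section 4.2 has no exclusion for a known earlier prolonged QTc, although the guidance cited in section 2.2 for omitting ECG screening names it as a high-risk feature

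*Protocol*

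**What the plan says.** Section 2.2 (Mitigation of Risk from HCQ and Azithro) states that the trial followed a published guidance and quotes it: "It may be reasonable to forego ECG screening to allow patients to remain in quarantine if no high-risk features exist". The features listed there are long QT syndrome, concomitant QT-prolonging drugs, structural or ischemic heart disease, "history of prolonged QTc on any ECG", and abnormal renal function or electrolytes. The protocol then draws its conclusion, beginning "Therefore, we will exclude potential participants with underlying conditions associated with TdP, including". The conditions that follow do not include a prolonged QTc on an earlier tracing. A preceding paragraph of the same section lists the trial's risk-reduction measures, among them excluding people who "have a personal or family history of Long QT syndrome, a history of ventricular arrhythmias"; it does not mention an earlier prolonged QTc either.

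In section 4.2 the nearest criterion is 4.2.4, "Personal or family history of Long QT syndrome". The section opens by noting that "Medical history can be by self-report". Section 6.3.4 gives a list under the instruction that "the following diagnoses should be recorded regardless of when the diagnosis was made"; it includes arrhythmias but not a prolonged QTc.

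Section 2.1 (Assessment of Potential Risks and Benefits) explains why no ECG is done at entry or on treatment and remarks that "exclusions on the basis of baseline QTc are unlikely to add significantly to" overall safety beyond the exclusions already planned.

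**The concern.** The protocol uses the guidance as part of its case for giving HCQ and azithromycin without an ECG, and that guidance is conditional. One of its conditions is not enforced by the eligibility criteria. Someone who has been told of a prolonged QTc, but never given a Long QT diagnosis, meets no exclusion and may receive both drugs.

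Entry history is the main protection for the individual participant here. No ECG is taken. Section 2.2 itself says that stopping treatment after QTc prolongation is found may achieve little because both drugs have long half-lives; section 2.1 gives 40 to 50 days as the terminal half-life for HCQ. Notifying the DSMB of torsades de pointes (TdP), ventricular arrhythmia or sudden death comes after the event.

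The result is also out of order. A relative's long QT syndrome excludes a person (4.2.4), and so does taking a magnesium supplement (4.2.7), but the person's own recorded prolonged QTc does not. The protocol does not explain this.

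**Working it through.** The protocol has no figure of its own to reproduce on this point. The check sets the features in the quoted guidance (section 2.2) against criteria 4.2.1 to 4.2.15.

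| Feature in the guidance | Matching criterion |
|---|---|
| Long QT syndrome | 4.2.4 (personal or family) |
| Concomitant QT-prolonging drugs | 4.2.10, with 4.2.11 for loop diuretics |
| Structural or ischemic heart disease | 4.2.6 |
| Prolonged QTc on an earlier ECG | none |
| Abnormal renal function or electrolytes | 4.2.5 and 4.2.7 |

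Unmatched: 1 of 5, or 1 of 6 if renal function and electrolytes are counted separately.

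Could another provision catch such a person?

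- **4.2.4.** Long QT syndrome is a diagnosis. The guidance lists it and an earlier prolonged QTc as two items, so the first cannot be read as covering the second. An acquired or incidental finding passes 4.2.4.
- **4.2.3.** This covers ventricular arrhythmia and antiarrhythmic use. A prolonged QTc is neither.
- **Investigator discretion within 4.2.** 4.2.1 concerns present need for hospital or immediate care, and 4.2.15 concerns drug or alcohol use. There is no general discretion criterion.
- **Clinical assessment at enrollment (6.3.6).** It looks for people ill enough to need further evaluation, not for a QTc history.
- **Medical history (6.3.4).** This is a recording list, and the item is not on it.

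Scale, under a stated assumption. Let p be the proportion of participants who know of an earlier prolonged QTc and meet no other exclusion. The protocol gives no value, so take p from 0.1% to 1%.

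- Expected number = 2000 × p: 2000 × 0.001 = 2, and 2000 × 0.01 = 20.
- With 1:1 allocation, half are on active drug: 2 / 2 = 1, and 20 / 2 = 10.

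For the size of the drug effect, the protocol gives a mean QTc increase of 28 ms (95% CI 18 to 38) with chloroquine in healthy adults (sections 2.1 and 2.2). From the azithromycin label it gives a maximum mean QTcF increase, relative to chloroquine alone, of 5 ms (upper bound 10) with 500 mg azithromycin (section 2.1). These are chloroquine data from two different sources. They should not be added together or read as HCQ estimates.

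**The case against.** The strongest reply is that section 2.1 already gives a judgement on exclusions based on QTc: they would add little beyond the planned exclusions for cardiac history, renal and liver disease, and QT-prolonging drugs. On that view the omission is a disclosed choice, and the same reasoning would extend to an earlier tracing. But the remark concerns baseline QTc, in a paragraph arguing against taking ECGs in the study. Its practical grounds are protective equipment and staff exposure, and a history question uses neither. The same sentence relies on excluding higher-risk people by personal cardiac history, which is the kind of criterion missing here.

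Other points have some force:

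- **The group left over is small.** Criteria 4.2.3 to 4.2.8, 4.2.10 and 4.2.11 remove many people with a reason for a long QTc, and the protocol regards TdP as very rare. This limits the size of the problem but does not close the gap.
- **The lists in section 2.2 are open-ended.** The second omits kidney disease, which 4.2.5 nevertheless excludes. Absence from those lists is weak evidence alone, but section 4.2 is the operative list and lacks the item too.
- **Other safeguards exist.** Section 5.4 requires review of the package insert, section 9.2 allows discontinuation at the investigator's discretion, and section 10.5 provides for DSMB notification. None is an eligibility rule.
- **The manual of procedures and the screening checklist are not available.** They might prompt the question, but they cannot replace an exclusion criterion.
- **The guidance is permissive, and sections 2.1 and 2.2 give other grounds for no ECG:** rarity of TdP, infection control, usual outpatient practice and discussion with the FDA. These explain not performing an ECG. They do not explain not asking about a result already known.
- **The head-count rests on an unsourced prevalence.** That is correct, and the conclusion does not depend on it.

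**Conclusion.** The concern holds. The protocol cites a condition for omitting ECG screening, and its eligibility criteria leave one of the five named features unaddressed. This follows from the text of sections 2.2 and 4.2 and needs no assumption. Only the count does: 2 to 20 participants, 1 to 10 of them on active drug, if 0.1% to 1% have such a known result and no other exclusion. The protocol gives no event risk for this group, so no number of harmful events can be derived. The affected group is probably small and the harm rare but serious. The point should be corrected because the correction is cheap; it does not affect the validity of the efficacy comparison. The creatinine clearance allowance in 4.2.5 is a stated threshold and is not part of this point.

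**What to change.** Add one exclusion to section 4.2: *known prolonged QTc on an earlier ECG (self-report accepted)*. Put the same item on the screening checklist and in the exclusion lists of section 2.2. If the sponsor prefers not to adopt it, section 2.2 should at least say why this feature of the guidance was set aside.

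The cost is one line in section 4.2, one checklist item and one phrase in section 2.2. No ECG or additional contact is needed, since section 4.2 already accepts self-reported history. The downside is losing a few otherwise eligible people at screening (2 to 20 under the assumption above). Section 10.4 sets the sample size as 2000 participants who take the first confirmed dose, so the target and the power do not change.

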3.0 STUDY DESIGN

This is a phase IIB, double-blind, placebo-controlled randomized trial, designed to compare the efficacy of HCQ and Azithro versus placebo to prevent hospitalization and death in symptomatic adult outpatients with COVID-19, **caused by SARS-CoV-2 infection**. The study is a multicenter trial that will be conducted in the United States.

A total of 2000 participants who start study treatment (approximately 1000 in each treatment arm) will be followed on study for 7 days on treatment and an additional 23 weeks off treatment. Participants who do not start study treatment will be replaced. Participants will be randomized 1:1 to receive either **400 mg orally twice a day on Day 0** followed by **200 mg orally twice a day for 6 days**, and Azithro/Placebo 500 mg **once on Day 0**, followed by 250 mg daily for four days ([Figure 3-1](#)).

Randomization will be stratified by “high” versus “low” risk of severe disease, where “high” risk is defined by any of the following:

- Persons aged 60 years and older
- Persons having at least one of the following conditions:
 - Chronic lung disease or moderate to severe asthma
 - Immunocompromised status due to disease (for example, those living with HIV with a CD4+ T-cell count of <200/mm³)

- Immunocompromised status due to medication (for example, persons taking 20 mg or more of prednisone equivalents a day, anti-inflammatory monoclonal antibody therapies, or cancer therapies)
- Severe obesity (body mass index [BMI] >40; may be based on self-report of height and weight)
- Hypertension
- Cardiovascular disease
- Diabetes
- Chronic kidney disease
- Chronic liver disease

[figure not shown]

Figure 3-1: Study Design

Recruitment

Participants can be recruited by sites in several ways, which will be enhanced because many clinical research sites (CRSs) are participating in COVID-19 screening activities. Thus, sites may work with local SARS-CoV-2 testing sites through outreach staff and recruitment materials placed at this location. It is also expected that participants will be referred to the study immediately upon SARS-CoV-2 diagnosis from partnering testing sites or ordering providers who receive test results. Symptomatic persons receiving a positive SARS-CoV-2 result by molecular test can be informed about the study opportunity and be provided with study site contact information.

Study Visits

The study is designed to minimize in-person contact between participants and study staff or other persons at the CRS. The informed consent process, screening, and randomization may be performed remotely, in compliance with institutional and regulatory requirements.

At study entry, all participants will have either a remote visit or an in-person study visit at a secure location of the CRS, such as an isolation room, a room with a separate

entrance, or while in their car in a parking lot/parking garage. Participants will be given study treatment, a study symptom and adherence diary (i.e., Study Diary), and contact numbers for the study staff. Participants will provide medical and medication histories, and contact information for themselves, including their home address, **a list of local hospitals where they are likely to seek medical services if needed**, and for persons who will know about their study participation, in case study staff cannot reach the participant. Further, participants will be provided contact information for research staff in the event they require hospitalization. Participants will then complete **the Pre-Treatment page** of the Study Diary prior to starting study treatment.

The participant's first symptom(s) associated with COVID-19 and when it/they occurred will be recorded. Participants will also be observed taking their first dose of study treatment if it is an in-person visit.

Participants will record their symptoms, temperature (if participant is able to provide), medication adherence, and major events such as hospital visits and hospitalization in the Study Diary daily on Days 0-20, **in the evening** ([section 6.3.10](#)). Study staff will contact participants per the Schedule of Evaluations ([SOE](#)) to review study diaries. If participants cannot be reached after two attempts 24 hours apart, then their alternative contact person(s) will be called.

At Day 20, **for non-sampling subset participants**, an in-person **or remote** visit will occur for assessment of the primary outcome and collection of the Study Diary. At this time the participants are expected to no longer be infectious, if they remain un-hospitalized. For participants that cannot **be reached**, the study staff will contact the alternative contacts the **participant** provided to collect information on these outcome measures. **If the participant is symptomatic on Day 20 and an in-person study visit was planned, the in-person study visit may be delayed (refer to [section 6.2.3](#)) or converted to a remote visit. If a remote Day 20 visit is conducted, arrangements should be made for future transfer of Study Diary from the participant to the study staff (i.e., mailing the Study Diary or sending images) and provision of compensation for study participation.**

At weeks 12 and 24, remote visits will be performed to review longer term disease course. At these visits, study staff will record any hospitalizations or deaths that occurred since the Day 20 visit. Additional approaches (such as querying death registries) may be used as feasible at the sites.

Participants will be instructed to contact study staff immediately if they seek medical help at any time during the study.

Additional Evaluation Subset

Some sites will be selected to conduct more in-person visits, depending on availability of staff, PPE, and isolation rooms.

At pre-selected sites, **at study entry [Day 0] and Days 6 and 20**, a subset of participants who agree will undergo self-collected nasal swabs, staff-collected NP swab,

and blood collection on site under appropriate infection control conditions, as described below. Single sparse pharmacokinetics (PK) sampling will be collected at Days 6 and 20 (refer to [section 11.0](#) for details).

Isolation Procedures

Given that SARS-CoV-2 is spread through respiratory droplets, each site must develop procedures to protect study staff and participants of other trials from infectious exposure. Each site will have a plan for maximal protection by providing PPE, setting up isolation rooms or outside areas, providing special access points or contact with study participants. Each site will develop their own set of procedures for such participant contact.

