6.2.2 Entry Evaluations

Screening and entry visits may be combined. The study entry visit **can be** either a remote or in-person visit. **Participants must begin study treatment within 96 hours of the collection time of the respiratory specimen that was positive for SARS-CoV-2 and qualified them for the study.** The first dose of study treatment must be directly observed at the in-person visit or confirmed remotely (by video or telephone) **for those with remote study entry visit. The day of the first dose is considered Day 0.**

Depending on how the screening and study entry/Day 0 visits are conducted, randomization must occur after screening but may occur prior to the study entry/Day 0 visit, or at the study entry/Day 0 visit.

Those participants that agree to the additional sample collection must have the NP swab, self-collected nasal swab, and blood collected prior to receiving the first treatment dose.

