6.2.3 Post-Entry Evaluations

On-Treatment Evaluations

Participants will undergo remote evaluations as outlined in the SOE, [section 6.1](#).

Those participants undergoing additional NP swab, self-collected nasal swab, and blood collection **will be required** to have in-person visits at Days 6 **and** 20.

Post-Treatment Evaluations

Participants will undergo remote evaluations as outlined in the SOE, [Section 6.1](#).

Participants not participating in the sampling subset will undergo **an in-person or remote** study visit on Day 20, as outlined in the SOE, [Section 6.1](#). **Subset participants will have an in-person study visit at Day 20.** The Day 20 visit may occur anytime during the window outlined in the SOE, [Section 6.1](#). For non-subset participants, Day 20 in-person visits should be performed only if the participant has been afebrile for at least 72 hours and other symptoms have improved. If these criteria are not met, the visit should be conducted remotely. **If a remote Day 20 visit is conducted**, arrangements should be made for future transfer of diary **from the participant to the study staff** and provision of compensation for study participation.

Study Completion Evaluations

Participants will undergo a remote evaluation at Week 24.

6.2.4 Discontinuation Evaluations**Evaluations for Participants Who Do Not Start Study Treatment**

Participants who are randomized but do not take the first (confirmed) dose of study treatment do not need to be followed. A study discontinuation eCRF must be completed and any evaluations completed for these participants should also be recorded on the Day 0 eCRFs.

Premature Treatment Discontinuation Evaluations

Participants who discontinue study treatment early should remain on study and all evaluations should be performed as outlined in the [SOE](#).

For participants consenting to the optional intensive sampling study, if the Day 0 CrCl result is <45 mL/min, as calculated by the Cockcroft-Gault equation (see Cockcroft-Gault calculator on the A5395 PSWP), the participant will be prematurely discontinued from study treatment.

Premature Study Discontinuation Evaluations

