6.3.10 Study Diary

Distribution of Study Diary

Participants will be provided a Study Diary at study entry. The Study Diary is posted on the DMC Portal in the Forms Management Utility.

Participants will be asked to keep a log of symptoms, temperature (if possible), medications they are taking, and major events such as urgent visit to an emergency room or clinic and hospitalization in their Study Diary on Days 0-20. At study entry, participants will complete the Study Diary prior to study treatment initiation. Depending on timing of each participant's dosing, some may complete HCQ/Placebo study treatment on Day 7 instead of Day 6 and need to report a Day 7 dose. Participants will be asked to complete the diary each evening.

Review of Study Diary

The Study Diary will be reviewed by study staff with each participant at the remote and in-person visits described in the [SOE](#) and the participant's answers recorded in the Participant Study Diary eCRF. If feasible, prior to or during the remote study visits, sites will request that the participant send images of each of their study diary entries to be reviewed at the next study contact.

Participants who report worsening illness from any cause during the trial may be referred to their health care provider or closest emergency room. Such instances will be recorded at the time of the notification, and during follow-up to assess study endpoints, i.e., hospitalization or death.

Review of Treatment Adherence

The treatment adherence portion of the Study Diary will be reviewed by study staff with each participant at the remote and in-person visits (if applicable), as described in the [SOE](#). The participant's answers of timing of doses taken will be recorded in the Adherence Assessment eCRF. If any doses are missed, the reason for the missed dose will be recorded.

Collection of Study Diary

The Study Diary will be collected per the [SOE](#). **If Day 20 is conducted remotely, arrangements should be made for future transfer of study diary from the participant to the study staff (i.e., mailing the study diary or sending images).**

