10.2.1 Primary Outcome Measure

Death from any cause or hospitalization during the 21-day period from and including the day of the first (confirmed) dose of study treatment. Hospitalization is defined as requiring at least 24 hours of acute care in a hospital or similar acute care facility, including Emergency Rooms or temporary facilities instituted

to address needs during the COVID-19 pandemic. Evaluation at a hospital or similar facility with less than 24 hours of acute care is not considered a hospitalization.

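### An in-person visit held during Day 20 collects the diary before its last evening entry is written and assesses the primary outcome before its 21-day window has closed

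*Protocol*

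**What the plan says.** - **Outcome window.** Section 10.2.1 defines the primary outcome as "Death from any cause or hospitalization during the 21-day period from and including the day of the first (confirmed) dose of study treatment". Section 6.2.2 fixes the start: "The day of the first dose is considered Day 0".
- **Hospitalization.** The same outcome section requires 24 hours of acute care: "Evaluation at a hospital or similar facility with less than 24 hours of acute care is not considered a hospitalization".
- **The visit.** Under section 3.0 a Day 20 "visit will occur for assessment of the primary outcome and collection of the Study Diary". Section 6.2.3 lets it take place at any time in the window given in the Schedule of Evaluations (SOE). It may be in person or remote for most participants, but must be in person for the sampling subset.
- **The diary.** Entries cover Days 0-20, and section 6.3.10 adds: "Participants will be asked to complete the diary each evening". After a remote visit the diary is sent in later, and section 6.3.8 puts a stamped envelope in the kit for this.
- **Uses of the diary.** Section 10.2.2 takes the fever duration, the symptom duration and the symptom-score AUC from it. The AUC runs explicitly through Day 20.
- **Later capture.** At Weeks 12 and 24, "study staff will record any hospitalizations or deaths that occurred since the Day 20 visit" (section 3.0).

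**The concern.** The contact meant to settle the primary outcome, and to collect the complete diary, can come before either is complete. At a daytime in-person visit on Day 20, three things are still open:

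1. The Day 20 evening diary entry has not been made.
2. The remaining hours of Day 20 have not been observed.
3. An admission that began within the previous 24 hours cannot yet be classed as a hospitalization or not.

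The first item affects the secondary diary outcomes directly, because the diary leaves the participant's hands. The other two affect how firm the primary status is at that contact. They also affect the interim efficacy reviews, which section 10.5 ties to follow-up for the outcome assessed at Day 20 and plans weekly from about 500 participants.

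**Working it through.** **Day count.** Day 0 to Day 20 inclusive is 20 − 0 + 1 = 21 days, so window and diary both end at the close of Day 20. The SOE visit-window row is broken in the text available. It is best read as 0/+7 (Days 20-27); the only other reading is +/-2. Both allow Day 20.

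**Diary.** One of 21 entries is 1/21 = 4.8%. With flat daily scores that is the share of the AUC affected; with falling scores it is less. A duration defined by the last day with a symptom or fever can be short by at most one day (Day 19 in place of Day 20). Outside the subset, section 6.2.3 allows an in-person visit only after 72 hours without fever and with other symptoms improved, so the missing entry falls mostly on people who are recovering. That restriction does not apply to the subset of about 200.

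**The plan's own power figure.** Inputs from section 10.4: 15% versus 10%, 1000 per arm, 5% lost to follow-up, so 950 per arm; two-sided 5%. Power = Φ[(δ − z·SE₀)/SE₁], where:

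- δ = 0.05
- SE₀ = √(2 × 0.125 × 0.875/950) = 0.01517
- SE₁ = √((0.15 × 0.85 + 0.10 × 0.90)/950) = 0.01513

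With z = 1.96 this gives 91.0%. With an assumed final nominal level of 0.043 for the four-look boundary it gives 89.9%. The stated 90% is reproduced.

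**Events still open at a Day 20 visit.** Expected events: 1000 × 0.15 + 1000 × 0.10 = 250. Assume a constant event rate over the 21 days and every visit held on Day 20 at the hour shown. Still to come is ((24 − h)/24)/21. Adding one day covers admissions that cannot yet have reached 24 hours.

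| Visit time | Still to come | Events of 250 | Including last 24 h | Events of 250 |
|---|---|---|---|---|
| 09:00 | 0.625/21 = 3.0% | 7.4 | 1.625/21 = 7.7% | 19.3 |
| 17:00 | 0.292/21 = 1.4% | 3.5 | 1.292/21 = 6.2% | 15.4 |

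A falling event rate lowers these. Events starting on calendar Day 20 number 11.9 if the rate is flat, 3.7 if it halves every 7 days and 1.3 if it halves every 4 days. For Days 19 and 20 together the figures are 23.8, 7.8 and 2.8.

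**First efficacy review.** With 500 participants, 250 × 0.15 + 250 × 0.10 = 62.5 events are expected. Under the flat rate, 62.5 × 1.4% to 62.5 × 3.0% is about 0.9 to 1.9 events still to come at the visit.

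**Worst case for power.** Suppose none of the open events were ever recovered and both arms lost the same share. Power would then be 88.3% to 90.5% at level 0.05, and 87.0% to 89.4% at 0.043. This is an upper limit on the harm, because the protocol has several ways of recovering these events.

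**The case against.** The strongest reply is that no primary event falls outside the capture rules. The Week 12 look-back starts at the Day 20 visit, so the two periods join, and an event on the evening of Day 20 is later recorded and counts in the 21-day analysis. Participants are told to contact staff at once if they seek medical help. Sites may use family, named hospitals, medical records and databases (section 6.3.13). An inpatient admission is also a serious adverse event, so an admission in progress can be resolved within a day. This stands: for the primary outcome the exposure is late or provisional status, not general loss.

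Two stronger readings are tempting but unsupported:

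- **That recovered participants are closed out before Day 20 ends.** Nothing in the protocol closes the endpoint record at Day 20. Follow-up runs to Week 24, and censoring at last known status (section 10.6.1) is for those who discontinue and cannot be contacted.
- **That sections 3.0 and 6.2.3 contradict each other on symptomatic participants.** Section 3.0 offers delay, with a reference to 6.2.3, or conversion to a remote visit. Section 6.2.3 allows any day in the window and says "If these criteria are not met, the visit should be conducted remotely". The two can be read together.

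It is also fair that the diary gap is limited to in-person visits held on Day 20 itself, that the outcomes affected are secondary and blinded, and that no difference between arms is shown. The manual of procedures, which is not at hand, may already say more on visit timing. None of this restores the Day 20 evening entry once the diary has been handed over.

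**Conclusion.** The point holds as a minor one. By the protocol's own day count, the visit may be held before the outcome window and the diary are complete. The certain consequence is the last of 21 diary entries, missing or made early, for anyone seen in person during Day 20, including subset participants seen that day. Remote visits avoid it.

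For the primary outcome, roughly 3 to 7 of 250 expected events could still lie ahead at daytime Day 20 visits. The figure is 15 to 19 if admissions not yet 24 hours old are counted. Both ranges assume a constant event rate and that everyone is seen on Day 20 itself, so they overstate what would occur with later or spread visits or a falling rate.

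A reader might infer that the trial loses power or that primary events go missing. The documents do not support this, since the later contacts and record searches recover most of them. Permanent loss is confined mainly to participants never reached again. There is also a small wording gap: the Week 12 question runs from a Day 20 visit that some participants will have missed, although the protocol does require attempts to reach them or their contacts.

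**What to change.** - In sections 3.0, 6.1 and 6.2.3, make Day 21 the earliest day for the endpoint contact and diary collection, for example Days 21-27. Leave the outcome window at Days 0-20.
- If subset swabs and blood stay on Day 20, let those participants keep the diary, return it in the stamped envelope already in the kit, and have a short endpoint call on or after Day 21.
- Word the Week 12 question to run from the last contact with known status.

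The cost is a few words in the protocol, an earliest closure one day later and, if subset sampling stays on Day 20, one short extra call for about 200 participants. Sample size, stated power and outcome definitions do not change.
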